1.2. Intended Use of Investigational Products

The proposed intended use of K-Lens, a daily disposable contact lens, is to provide vision correction while preventing ocular itching associated with allergic conjunctivitis. The prevention of itch has been demonstrated to last through 12 hours in clinical studies; however, the contact lens may be worn for longer than 12 hours for vision correction.

The intended users are phakic or aphakic patients who are suitable for contact lens wear and experience ocular allergic itch due to allergic conjunctivitis and who do not have red eye(s) or more than 1.00 D of astigmatism.

1.3. Summary of Findings from Nonclinical Studies

K-Lens was shown to be biocompatible and tolerable on eye. Specifically, K-Lens extracts were shown to be non-cytotoxic, non-ocular irritating and non-sensitizing. The extracts of K-Lens in a packing solution were not mutagenic. K-Lens placed on rabbit eyes has been shown to be non-irritating and non-toxic to the eye, and without systemic toxicity following a minimum seven hours of daily lens wear for up to 6 months.²¹

All previous pre-clinical findings were deemed satisfactory prior to proceeding with clinical trials on humans.

For the most comprehensive nonclinical information regarding K-Lens, refer to the latest version of the Investigator's Brochure.²¹

1.4. Summary of Known Risks and Benefits to Human Subjects

K-Lens has been evaluated for safety, tolerability, and efficacy (prevention of ocular itching) in previous studies.⁹⁻²⁰

The results from the Phase 3 safety trials for K-Lens have shown that the risks to wearing K-Lens are not substantially increased as compared to other non-medicated contact lenses worn in a daily disposable modality or the use of ketotifen fumarate ophthalmic drops. The ocular adverse events with the highest reported incidence from the Phase 3 safety trials were instillation site irritation (3.7%), dry eye (0.9%), eye irritation (0.8%). All non-ocular adverse events from the two Phase 3 safety trials were assessed by the Investigators as not related to study medication.

The benefits of K-Lens include the correction of refractive error and the prevention of itch associated with allergic conjunctivitis.

For the most comprehensive clinical information regarding K-Lens refer to the latest version of the Investigator's Brochure.²¹

1.5. Relevant Literature References and Prior Clinical Data Relevant to Proposed Clinical Study

K-Lens is an investigational drug/device combination product and the clinical results have yet to be published. Additionally, there are no known publications reporting clinical data with a contact lens containing an anti-allergy medication.

K-Lens has been evaluated in previous studies.⁹⁻²⁰ for safety, tolerability, and efficacy (prevention of ocular itching). Additionally, in the previous K-Lens studies, visual acuity was assessed using Snellen visual acuity charts which are commonly used in clinical practice. The proposed clinical study will assess visual acuity using logMAR (ETDRS) charts which are more commonly used in clinical research studies. By collecting data from both types of visual acuity charts, a more comprehensive assessment of visual acuity with K-Lens will be obtained.

For additional clinical information regarding K-Lens, refer to the latest version of the Investigator's Brochure.²¹

2. STUDY OBJECTIVES, ENDPOINTS AND HYPOTHESES

2.1. Objectives

The purpose of this study is to evaluate the clinical performance of K-Lens produced on the new J&J Vision Care, Inc. manufacturing line in Limerick, Ireland.

2.2. Endpoints

Primary Endpoint

The primary endpoint is monocular contact lens-corrected distance visual acuity using a logMAR visual acuity scale. This will be evaluated under high luminance and high contrast conditions at 4 meters from ETDRS charts at the 1-week follow-up visit.

Secondary Endpoint(s)

- Proportion of eyes with clinically significant (Grade 3 or 4) slit lamp findings.
- Proportion of eyes with unacceptable lens fitting.

Other Endpoints

Average daily wear time (in Hours):

Average daily wear time will be calculated as the number of hours between subjects reported time of insertion and time of removal of the study lenses, on an average day, at 1-Week Follow-up evaluation.

Subjective assessment of lens handling:

Lens handling will be assessed using Contact Lens User Experience™ (CLUE) questionnaire at 1-Week Follow-up evaluation. CLUE™ is a validated patient reported outcomes (PRO) questionnaire to assess patient-experience attributes of soft contact lenses (comfort, vision, handling, and packaging) in a contact-lens wearing population in the US, ages 18-65. Derived CLUE™ scores using Item Response Theory (IRT) follow a normal distribution with a population average score of 60 (SD 20), where higher scores indicate a more favorable/positive response with a range of 0-120. A 5-point increase in an average CLUE™ score translates into 10% shift in the distribution of scores for population of soft contact lens wearers.²²

Slit-lamp findings:

Frequency and severity by eye of slit lamp findings (SLFs) including conjunctival injection, corneal edema, corneal neovascularization, corneal staining, tarsal abnormalities or any other complications. SLFs will be evaluated at fitting and post-fitting evaluation visits including unscheduled visits.

Subject's Reported Ocular Symptoms:

Frequency and severity by eye of subject's reported ocular symptoms and problems with the study lens at fitting and post-fitting evaluation visits including unscheduled visits.

Lens fitting characteristics:

Frequency by eye of mechanical lens fitting characteristics including lens centration and lens movement and overall lens fitting acceptability at fitting and 1-Week Follow-up evaluations.

Adverse events, number and reasons for discontinuation, number and reasons for unscheduled lens replacement including lens damage will be monitored and descriptively evaluated.

2.3. Hypotheses

Primary Hypotheses

The K-Lens will be non-inferior to the Placebo lens with respect to monocular distance contact lens-corrected visual acuity. A non-inferiority margin of 0.1 logMAR (one line) units will be used.

3. TARGETED STUDY POPULATION

3.1. General Characteristics

The study populations will be healthy normal habitual contact lens wearers that are at least 18 years old and less than 40 years old.

3.2. Inclusion Criteria

Potential subjects must satisfy all of the following criteria to be enrolled in the study:

1. The subject must read, understand, and sign the STATEMENT OF INFORMED CONSENT and receive a fully executed copy of the form

2. Appear able and willing to adhere to the instructions set forth in this clinical protocol
3. Between 18 and 39 (inclusive) years of age at the time of baseline visit
4. The subject must be a habitual lens wearer for a least 6 days/week and for a minimum of 8 hours per day over the last month.
5. The subject's contact lens correction must be in the range of -1.00 D to -6.00 D (inclusive) in each eye.
6. The subject's refractive cylinder must be 1.00 D or less in each eye
7. Have a spherocylindrical best corrected visual acuity of 20/30 or better in each eye (Snellen Visual Acuity)

3.3. Exclusion Criteria

Potential subjects who meet any of the following criteria will be excluded from participating in the study:

1. Currently pregnant or lactating
2. Any systemic disease (e.g., Sjögren's Syndrome), allergies, infectious disease (e.g., hepatitis, tuberculosis), contagious immunosuppressive diseases (e.g., HIV), autoimmune disease (e.g. rheumatoid arthritis), or other diseases, by self-report, which are known to interfere with contact lens wear and/or participation in the study
3. Use of systemic medications (e.g., chronic steroid use) that are known to interfere with contact lens wear
4. Any ocular allergies, infections or other ocular abnormalities that are known to interfere with contact lens wear and/or participation in the study. This may include, but not be limited to entropion, ectropion, extrusions, chalazia, recurrent styes, glaucoma, history of recurrent corneal erosions, aphakia, or corneal distortion
5. Any corneal distortion resulting from previous hard or rigid gas permeable contact lens wear, history of strabismus, or current monovision, multi-focal, or toric contact lens correction.
6. Any current use of rewetting drops or ocular medication
7. Any previous, or planned (during the course of the study) ocular surgery (e.g., radial keratotomy, PRK, LASIK, etc.)
8. Any Grade 3 or greater slit lamp findings (e.g., edema, corneal neovascularization, corneal staining, tarsal abnormalities, conjunctival injection) on the FDA Biomicroscopy Scale
9. Any previous history or signs of a contact lens-related corneal inflammatory event (e.g., past peripheral ulcer or round peripheral scar), or any other ocular abnormality that would contraindicate contact lens wear
10. Any known hypersensitivity or allergic reaction to ketotifen
11. Participation in any eye drop, contact lens or lens care product clinical trial within 14 days prior to study enrollment
12. Employee or immediate family member of an employee of clinical site (e.g., Investigator, Coordinator, Technician)

3.4. Enrollment Strategy

Study subjects will be recruited from the Institution/clinical site's subject database and/or utilizing Independent Ethics Committee (IEC) or Institutional Review Board (IRB) approved materials.

4. STUDY DESIGN AND RATIONALE

4.1. Description of Study Design

This is a randomized, double masked, bilateral, controlled, two-arm parallel group, multi-site, 1-week dispensing study. Approximately 132 subjects will be screened and randomly assigned to either K-Lens or Placebo using 2:1 ratio (i.e. 2/3 of subjects on the K-Lens arm and 1/3 on the Placebo arm). The goal is for a sample size of 120 (80 subjects in K-lens and 40 subjects in Placebo) after subjects who withdraw or are lost-to-follow-up.

The study begins with an Initial Visit (Visit 1). If a subject is found to meet all eligibility criteria (see Section 34.), they will be randomized and fit with either the K-Lens or Placebo lens in both eyes based on the randomization scheme provided to the investigators; otherwise, the subject will be deemed ineligible for this study.

Successfully dispensed subjects at the initial visit will be scheduled for a follow-up visit (Visit 2). The follow-up visit will occur approximately 6 to 9 days after the Initial Visit. Unscheduled follow-up visits may occur during the study. Subjects will be advised to wear the study lenses at least 8 hours a day for a minimum of 6 days.

Both study lenses will be worn as a daily disposable modality. J&J Vision will provide the investigational sites with sufficient quantities of study lenses and supplies to complete the study.

The Investigator is responsible for ensuring that all subjects entering the study conform to subject selection criteria. The number of subjects targeted for randomization and completion are as follows:

Table 1: Target number of subjects by arm and site

	K-Lens	Placebo	Total
Randomization	88	44	132
Completion	80	40	120
Number of sites	6	6	6
Subjects/site (Min-Max)	12-16	5-9	20-24

4.2. Study Design Rationale

Randomized, double masked, controlled designs are the gold standard to perform scientifically sound evaluations of the intervention by reducing bias associated with the conduct and interpretation of a clinical trial and avoiding confounding from other factors. The unequal

assignment using 2:1 K-Lens versus Placebo ratio was considered to gain additional information on the K-Lens produced on the new JJVC manufacturing line in Limerick, Ireland.

4.3. Enrollment Target and Study Duration

- This study will target to enroll approximately 132 subjects (88 subjects in K-lens arm and 44 in Placebo arm) with a minimum of 120 subjects to complete (80 subjects in K-lens arm and 40 in Placebo arm).
- Subjects will be considered enrolled in this trial only after they have reviewed and signed the informed consent.
- The study duration will be approximately 8 weeks and there will be a total of 2 visits

5. TEST ARTICLE ALLOCATION AND MASKING

5.1. Test Article Allocation

Subjects will be randomly assigned to either K-Lens or Placebo arm based on a computer-generated randomization schedule prepared before the start of the study. The randomization will be stratified by investigational site and randomly permuted blocks of 3 assignments will be used to achieve 2:1 K-Lens versus Placebo ratio within each study site.

Randomization must be performed at the initial visit. The following must have occurred prior to randomization:

- Informed consent has been obtained
- It has been determined that the subject meets all the inclusion / exclusion criteria
- Subject history and baseline information has been collected

When the trial fitting assessment is ready to be conducted, the following steps should be followed:

1. Investigator or designee (documented on the Delegation Log) will consult the randomization scheme to obtain the study test article assignment for that subject prior to dispensing.
2. Investigator or designee will record the subject's number on the appropriate line of the randomization scheme.
3. Investigator or designee will pull the appropriate test articles from the study supply. All test articles that were opened, whether dispensed or not, must be recorded on the Test Article Accountability Log in the "Lenses Dispensed" section.

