See Electronic Signature Report _____ Date
[name] _____
Senior Principal Research Optometrist

Clinical Operations
Manager

See Electronic Signature Report _____ Date
[REDACTED]
[REDACTED]

Biostatistician

See Electronic Signature Report _____ Date
[REDACTED]
[REDACTED]

Data Management

See Electronic Signature Report _____ Date
[REDACTED]
[REDACTED]
[REDACTED]
[REDACTED]

Reviewer

See Electronic Signature Report _____ Date
[REDACTED]
[REDACTED]

Approver

See Electronic Signature Report _____ Date
[REDACTED]
[REDACTED]

CHANGE HISTORY

Version	Originator	Description of Change(s) and Section Number(s) Affected	Date
1.0	[name]	Original Protocol	10 August 2017
2.0	[name]	
Section 2.2 – updated Secondary Endpoint to “clinically significant (Grade 3 or 4) slit lamp findings.”
 
Section 6.4 – updated lens packaging information.
 
Section 14.2 – updated reference information and changed Table 1 to Table 4. Updated TOC.
 
Section 14.6 – Added section number for Secondary Analysis and updated to “Secondary endpoints will be summarized descriptively using all available data including data from unscheduled visits.”
 
Updated protocol version and date throughout.
	19 September 2017
3.0	[name]	
Figure 1 – updated study flowchart to clarify lens modification procedures
 
Section 7.2 – Updated Visit 1 instructions on Step 1.13 and 1.16 to clarify lens modification procedures.
 
Updated protocol version and date throughout
 
Section 5.2 - Removed the specific randomization letter codes
 
New medical monitor assigned to the study
 
Appendix C – Added package insert
	31 October 2017

SYNOPSIS

[figure not shown]
Protocol Title	Clinical Evaluation of etafilcon A with ketotifen
Sponsor	Johnson & Johnson Vision Care, Inc., [name]
Clinical Phase	Developmental phase: Phase 2
Trial Registration	This study will be registered on ClinicalTrials.gov by the Sponsor
Test Article(s)	Investigational Products: K-Lens: etafilcon A with 0.019 mg ketotifen Placebo: 1-Day ACUVUE® Brand Contact Lens
Wear and Replacement Schedules	Wear Schedule: Daily Disposable Replacement Schedule: Daily
Objectives	The purpose of this study is to evaluate the clinical performance of K-Lens produced on the new J&J Vision Care, Inc. manufacturing line in Limerick, Ireland.

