5.2. Masking

This is a double-masked study where subjects, investigators are masked to the identity of the study lenses during the study period. Every attempt will be made to keep the other clinical trial personnel involved in the study (e.g. Data management, Biostatistician and Clinical Operations) unaware of the identity of the study lenses. The identity of the study lenses will be masked by over labeling the blister packs with a label containing the study number, lot number, sphere power, expiration date and the randomization codes. Only the personnel involved in the over labeling and the Statistician generating the randomization scheme will

have access to the decode information translating the randomization codes into K-Lens and Placebo arms. The medical monitor will also have access to the decode information in case breaking the mask is necessary for the urgent medical treatment of a subject.

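### A fixed, published block of 3 on a site-held list, with lot number and expiry on the masked label, leaves the arms potentially inferable at the site

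*Protocol*

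**What the plan says.** - **Allocation.** Protocol 5.1 and SAP 4.2 both state that "randomly permuted blocks of 3 assignments will be used to achieve 2:1 K-Lens versus Placebo ratio within each study site". No other block size is given, so each block holds two K-Lens and one Placebo.
- **List.** Under Protocol 4.1, eligible subjects are randomized and fitted "based on the randomization scheme provided to the investigators". Under 5.1 the investigator or designee "will consult the randomization scheme to obtain the study test article assignment for that subject prior to dispensing" and enters the subject number "on the appropriate line of the randomization scheme". Then "Investigator or designee will pull the appropriate test articles from the study supply". No central release, sealed envelope or separate dispenser is described. Step U.6 in 7.3 sends the site back to the scheme when extra lenses are needed.
- **Label.** Under Protocol 5.2 the blister packs carry "a label containing the study number, lot number, sphere power, expiration date and the randomization codes".
- **Key.** Protocol 5.2 also limits who can turn codes into arms: "Only the personnel involved in the over labeling and the Statistician generating the randomization scheme will" hold that key, with the medical monitor added for emergencies.
- **Codes.** The number of codes per arm is not given. The change history for version 3.0 records "Section 5.2 - Removed the specific randomization letter codes", so leaving them out of the current text was deliberate.
- **Outcome.** Under SAP 3.2.1 the investigator enters the letters missed and the eCRF derives the logMAR score. Nothing requires the person who handles the list to be different from the person who tests acuity.

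**The concern.** At 2:1, three is the smallest block possible. Here it is the only size used, and it is printed in a document that sites hold. The unequal ratio adds a second route: if codes are few, counting them tells the arms apart, which it would not do at 1:1. Lot number and expiry could add a third route if they differ by product.

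A site that knows the next arm can influence who is entered. A site that knows the current arm can influence how hard a subject is pressed for one more letter, how fit is graded, and whether the investigator approves dispensing (Protocol 7.2, step 1.21). That last decision also affects who reaches the per-protocol set used for the primary analysis. In a non-inferiority test, any of these acting in favour of K-Lens pushes towards a false claim.

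**Working it through.** **Inputs.** Block of 3 at 2:1 within site (Protocol 5.1). Six sites of 20-24 subjects and 80/40 completers (Protocol 4.1, Table 1). Margin 0.1 logMAR, one line (2.3). Two-sided alpha 0.05, so 0.025 for the upper bound, and planning SDs of 0.05 and 0.1 (14.2, Table 4). Five letters per line (SAP 3.2.1), so one letter = 0.1/5 = 0.02 logMAR. The documents give no figure for predictability or for bias from unmasking.

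**Step 1: check the test against the plan's own figure.** A two-sample non-inferiority t-test (noncentral t, one-sided 0.025, 2:1, totals in multiples of 3) at difference 0.04 and SD 0.1 first reaches 85% power at n = 117, as Table 4 states. At 120 the power is 86.7%.

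**Step 2: one code per arm.** In any complete block the K-Lens code appears twice and the Placebo code once. One complete block therefore identifies K-Lens, and 100% of assignments are known. A larger block does not help, because the commoner code is still K-Lens.

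**Step 3: several codes per arm.** Suppose one subject's arm becomes known, for example through emergency unmasking or a recognised lot. A known Placebo subject makes the other two in that block K-Lens. A known K-Lens subject leaves one of each, undetermined.

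**Step 4: share of assignments that are certain, given that all earlier arms at the site are known.** In a block of 3 the first assignment is never certain, the second is certain if the first was Placebo (probability 1/3), and the third always is:

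(0 + 1/3 + 1)/3 = 4/9 = 44.4%.

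| Block scheme | Certain share |
|---|---|
| Fixed 3 | 44.4% |
| Fixed 6 | 28.9% |
| Fixed 9 | 21.4% |
| Any, codes opaque | 0% |

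At 22 subjects per site, fixed blocks of 3 give 42.4% and a random mix of 3, 6 and 9 gives about 3.4% (simulation; the observer knows the set of sizes and all past arms). Best-guess accuracy falls less, from 77.3% to about 73%, against 66.7% for always guessing K-Lens.

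**Step 5: illustration of the effect on the test.** Assume that knowing the arm shifts the difference by one letter (0.02) in favour of K-Lens, that every subject is decoded, and that K-Lens is truly worse by exactly the margin. The critical value is t(0.975, 118) = 1.980.

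- SD 0.10: SE = 0.10 × √(1/80 + 1/40) = 0.0194; noncentrality 0.02/0.0194 = 1.03. False non-inferiority rises from 2.5% to 17.5%.
- SD 0.05: SE = 0.0097; noncentrality 2.07. It rises from 2.5% to 53.5%.

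**The case against.** The strongest reply is that no leak is demonstrated. The documents do not say how many codes each arm has, whether the printed lot is a manufacturing lot or a study lot, how lots map to products, or whether later lines of the scheme are visible. The key is restricted, and silence about codes in a site-facing document is good practice. Consent, eligibility and baseline must be complete before randomization. Acuity is recorded letter by letter and scored in the eCRF, and a designee may handle the list. The two lenses share base curve, diameter, powers and Dk (Protocol 6.1), so recognising a product needs a route that is not described.

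Most of this stands. A reader might infer that the arms are exposed whatever the coding, because lot and expiry would regroup several codes into two products. The documents do not support that. Product-specific lots are plausible, since only one lens contains ketotifen, but this is not stated, and lots may also differ by power.

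A reader might also take 44% as the share a site will know. It holds only once earlier arms are known.

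Nor can the one-letter shift simply be scaled by 44%. Across the three possible blocks, 3 of 6 K-Lens assignments are forced (50%) but only 1 of 3 Placebo assignments (33%). The earlier subjects who make the forcing possible are themselves identified by the time acuity is scored.

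The reply does not dispose of the avoidable part. A restricted key does not prevent inference from the list or the label, the procedures do not separate dispenser from assessor, and publishing the block size serves no purpose at the site.

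**Conclusion.** The arms are potentially inferable at the site; the documents do not establish that they are exposed. The share of assignments known ranges from 0% while codes stay opaque to 100% with one code per arm. Where arms leak by some other route and all earlier ones at the site are known, 44% of assignments are certain with the planned blocks.

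The rise in type I error from 2.5% to 17.5% (SD 0.10) or 53.5% (SD 0.05) rests on an assumed one-letter bias, complete decoding and a true difference at the margin. The documents supply none of these, and the planning differences are 0 to 0.04. The figures show how sensitive the test would be and do not predict what will happen. The point is worth acting on because the protection is inexpensive before the first subject.

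**What to change.** Before the first subject is randomized:

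1. Vary the block size at random (for example 3, 6 and 9) and move the sizes from Protocol 5.1 and SAP 4.2 to the restricted randomization file. Alone, this does not protect a site-held list with one code per arm.
2. Use several codes per arm in proportion to 2:1 (for example four for K-Lens and two for Placebo), so that each code appears equally often and counting reveals nothing. Release assignments one at a time, keeping each released code available for resupply under step U.6. One-at-a-time release alone is not enough, because released codes accumulate. Subject-numbered kits would be stronger but harder to supply, because lens power is chosen at Visit 1 (step 1.12).
3. Print a masked study lot number and one common expiry date on the over-label, unless the printed lot is already a study lot. Keep the true lots in the decode file so that complaint tracing under Protocol 12 still works.

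At the least, record in a restricted document the number of codes per arm, how lots map to products, and who can see the list.

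**Cost.** A new randomization file, slightly looser 2:1 balance within sites of 20-24, some relabeling across 21 powers (-1.00 to -6.00 D in 0.25 D steps: 5.00/0.25 + 1), and the earliest expiry governing all stock.
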